1.1 Title

A Randomised Controlled Trial of Low-Intensity Online Intervention (LiON) for Distressed Youths in Hong Kong

2. Background information

Youth marks a period of significant life transitions. Despite being a phase of optimal physical health, young people are often most vulnerable to the development of psychiatric symptoms and disorders. Studies have found up to 75% of mental disorders in adulthood have their onset before the age of 25 (Lin et al., 2008; Kessler et al., 2005), suggesting youth marks a critical period of intervention. Across the various psychiatric conditions, depressive and anxiety disorders have consistently been reported to be two of the most common conditions in young people globally (Merikangas et al., 2010; Racine et al., 2021).

Both depressive and anxiety disorders are related to various negative impacts on youths' lives, such as undermining academic achievements, with other negative influences found in past studies (Birmaher et al., 1996; Fletcher, 2008, Woodward and Fergusson, 2001; Swan and Kendall, 2016). Notably, an increasing number of studies have found not only can clinical disorders, but also early symptoms of such conditions, can cause significant burden on the individual, their family and peers, as well as the larger society (Spencer et al., 2018; Lynch and Clarke, 2006; Wingrove and Rickwood, 2020).

 Existing healthcare services, however, tend to prioritise service targeting those with severe mental health needs. Knowledge about subtle mental health symptoms is lacking among the general public, which can contribute to delayed care and treatment (Fung et al., 2021). In addition, mental health services in Hong Kong are not only characterised by long waiting times but are also coupled with significant stigma, which can in turn prevent help-seeking, especially among young people (Sun et al., 2017; Yap, Wright, and Jorm, 2011).

2.1 Mental health needs in Hong Kong

The Hong Kong population has undergone a series of highly stressful events traceable since June 2019, from large-scale social unrest to the local outbreak of Coronavirus disease 2019 (COVID-19) in January 2020, and more recently a fifth wave of COVID-19 cases since February 2022. Local studies have shown significant levels of depressive and anxiety symptoms in the local population resulting from such large-scale population-level stressors and other personal life stressors, particularly in young people (Ni et al., 2020; Wong et al., 2020).

In addition, the city has recently reported daily local positive COVID-19 cases as high as 50,000 during the fifth wave of the epidemic (as of March 2022). Increasingly stricter social distancing policies related to the COVID-19 situation has as a result been put in place, such as compulsory COVID-19 testing, mandatory quarantine at home or specified quarantine centres, temporary closure of certain venues, changes to school schedules, and other changes to work patterns. Health services have either become overwhelmed or suspended under the strain of COVID-19; the waiting time for non-urgent health services has also been further lengthened as a consequence, including mental health services. The majority of in-person interventions and services have also been switched to online modes whenever possible to reduce in-person contacts.

2.2 Significance of low-intensity online-based interventions for young people

In view of the significance of early engagement and intervention for those with mental health needs and the current situation in Hong Kong, the implementation of low-intensity online-based interventions (LiON) for mental health appears to be a largely promising approach.

Low-intensity refers to low usage of "specialist therapist time" (Bower and Gilbody, 2005), or usage in a cost-effective way, such as in a group-based Cognitive Behavioural Therapy (CBT) context). Low-intensity interventions focus on delivering self-help and self-management skills which can be led by non-specialists, which in turn help to reduce the cost required in both training and the delivering of intervention. Recent studies have also increasingly highlighted young people's preference to access mental health services through online platforms (Becker et al., 2016).

58 59

60

61

Due to limited mental health resources and the high demand for mental health services in Hong Kong, such online-based low-intensity interventions - when shown to be effective - can be largely helpful in reducing societal costs, reduce the barriers to help-seeking, and facilitate large-scale implementation of mental health services on a population level.

62 63 64

65

2.3 The current study

66 67 68

In order to investigate the efficacy of LiON in reducing symptoms of depression, anxiety, and distress in young people, a wait-list control randomised controlled trial (RCT) design will be adopted in this study. The effectiveness of this low cost approach in improving functioning, perceived sleep quality, stress coping abilities, and general self-efficacy will also be examined.

69 70

71

72

73

74

3. Study objectives and purposes

3.1 Study aims

The current study aims to evaluate the effectiveness of LiON, as compared with the control group, in reducing (1) depressive and anxiety symptoms, (2) distress symptoms, (3) perceived stress, as well as in (4) improving functioning, (5) sleep quality, (6) stress coping abilities, and (7) general self-efficacy in young people in Hong Kong.

75 76 77

3.2 Study outcomes

78 79 80 All measures of this study will be conducted at baseline, i.e., pre-intervention (To), post-intervention (T1), and 1-month follow-up (T2). The time frame will be past month for To assessments and past week for both T1 and T2 assessments. Basic demographics will also be collected at baseline.

81 82

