3.2.1 Primary outcomes

83 84 Primary outcomes of this study include improved symptoms of depression, anxiety, and distress at postintervention (T1) and 1-month follow-up (T2).

85 86

87

88

89

90

Symptoms of depression and anxiety will be assessed using the depression and anxiety subscales (DASS-D and DASS-A, respectively) of the 21-item Depression Anxiety Stress Scale (DASS-21; Lovibond & Lovibond, 1995). The DASS-D and DASS-A each contains 7 items that asks participants about their symptoms of depression and anxiety, respectively, using a 4-point Likert scale (from "did not apply to me at all" [o] to "apply to me very much, or most of the time" [3]). The final score for each subscale was generated by multiplying the sum of the individual items by a value of 2, yielding a score range from 0 to 42, with a higher score indicating higher severity.

95

96

Symptoms of distress will be assessed using 6 items from the Kessler Kessler Psychological Distress Scale (Kessler et al., 2002). Items were rated on a 5-point Likert scale (from "none of the time" [0] to "all of the time" [4]) and summed to generate the final distress score. The total score ranges from 0 to 24, with a high score indicating greater distress.

97 98 99

100

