3.2.2 Secondary outcomes

Secondary outcomes of this study include functioning (two items from the Kessler Psychological Distress Scale on days of reduced and lost productivity), perceived sleep quality (1 item from the Pittsburgh Sleep Quality Index [PSQI]), perceived stress level (single item Subjective Level of Stress [SLS-1]), stress coping abilities (Brief Resilience Scale [BRS]) and general self-efficacy (General Self-Efficacy Scale [GSE]). Information about the assessments is summarised in the table provided in Appendix A.

105 106

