3.3 Hypotheses

107 108 109

• Those in the LiON group, as compared to the control group, will show greater reductions in (1) depressive and anxiety symptoms, (2) distress symptoms, and (3) perceived stress.

110

Those in the LiON group, as compared to the control group, will also show greater improved (4) functioning, (5) perceived sleep quality, (6) stress coping abilities, and (7) general self-efficacy.

111 112

4. Study design, randomisation, and recruitment

[figure not shown]
113

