The findings of our pilot study (n = 34) suggested that LiON yields an effect size of 0.4 when compared with controls with no intervention at all. To test the main hypothesis that LiON is more effective in reducing participant's distress level than online self-help tips, we estimate the effect size could be halved, with alpha = 0.05 and power = 80%, 52 subjects are needed for each group totalling 104 subjects. After accounting for a 15% attrition, we target 120 subjects for the current study.

7. Statistical Analysis

All statistical analyses will be carried out using IBM® SPSS® with the significance level set at 0.05. Repeated measure ancova model will be used to compare the changes of distress level between two groups with adjustment for the variables that exhibit baseline differences.

A planned analysis will take place after data is available for the first 60 subjects, to provide a more accurate estimate of the power of the study to adjust the final sample size and allocation to the study arms, according to the principles of adaptive trial design.

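### Baseline uses a past-month recall window and follow-up a past-week window, so change from baseline, though not the randomised contrast at T1, mixes real change with a change of question

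*Protocol*

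**What the plan says.** Protocol section 3.2 begins "All measures of this study will be conducted at baseline" and adds the post-intervention (T1) and 1-month (T2) visits. It then fixes the windows: "The time frame will be past month for To assessments and past week for both T1 and T2 assessments". It exempts no measure and describes no rescaling.

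Other sections bring T0 into the outcome:

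- Section 3.2.1: "Primary outcomes of this study include improved symptoms of depression, anxiety, and distress", at both T1 and T2.
- Section 3.3: the LiON group, compared with control, "will show greater reductions in (1) depressive and anxiety symptoms, (2) distress symptoms, and (3) perceived stress".
- Section 7: "Repeated measure ancova model will be used to compare the changes of distress level between two groups". Covariates are chosen by observed imbalance: "with adjustment for the variables that exhibit baseline differences". The baseline score is therefore not fixed as a covariate; it enters only if it happens to differ between arms.

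The scales differ in how the window acts on them. For the 6-item distress score, "The total score ranges from 0 to 24, with a high score indicating greater distress", and each DASS-21 subscale runs from 0 to 42; these ranges do not depend on the window. The secondary functioning outcome is a count: "two items from the Kessler Psychological Distress Scale on days of reduced and lost productivity".

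Section 4.1 states that the wait-list arm receives its own 4-week LiON before T2.

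**The concern.** A symptom score for the past month and one for the past week answer different questions. If T0 uses one and T1 and T2 the other, the difference from T0 combines any real change with the effect of shortening the window. That matters wherever a result is read as improvement from baseline.

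T2 is the exposed visit. Improvement at T2 is a primary outcome, but both arms have received LiON by then. The arm comparison at T2 is early against delayed LiON, not LiON against control. A statement that participants have improved from baseline at T2 therefore rests on T0-to-T2 change within an arm, which is the quantity the window change affects.

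For the two productivity items the problem is mechanical: a count over about a month is set against a count over 7 days.

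**Working it through.** The protocol gives no figure for this point, so there is none to reproduce. The inputs are the windows (section 3.2), the day-count items (section 3.2.2), the change-based analysis (section 7) and 52 analysed per group (section 6). The month length (28 or 30 days), daily rates, correlations and effect size below are assumptions.

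**1. Does the window change bias the arm comparison?** Section 4.3 describes T0 ahead of randomisation, so T0 has the same expected value in both arms. Then

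E(T1 − T0 | LiON) − E(T1 − T0 | wait list) = E(T1 | LiON) − E(T1 | wait list).

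T0 drops out, whichever window it used, and T1 uses the same window in both arms. A simulation agrees. It ran 3000 trials with 52 per arm and no treatment or time effect; each person's daily rate came from Beta(1,4), with T0 binomial over 30 days and T1 binomial over 7.

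- Between-arm test of change: rejected in 4.7% of trials, the nominal level.
- Within-arm test of T0-to-T1 change: significant in 100% of trials, although nothing had changed.

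**2. Size for the day counts.** Expected count = daily rate × window length. With an unchanged rate, the apparent fall is 1 − 7/W for a month of W days:

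- W = 28: 1 − 7/28 = 75%.
- W = 30: 1 − 7/30 = 76.7%.

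| Share of days affected | T0 (30 days) | T1 (7 days) | Apparent fall |
|---|---|---|---|
| 10% | 3.0 | 0.7 | 2.3 days |
| 20% | 6.0 | 1.4 | 4.6 days |
| 33% | 10.0 | 2.3 | 7.7 days |

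The percentage fall is the same at every rate. With equal windows, or with days expressed as a proportion of the window, the artefact is zero.

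**3. What a raw change score on days would do.** Let the T0 SD be 1 and the T1 SD be k = 7/W, with correlation ρ and a true effect of d in T1 SD units. The standardised effect on raw change is

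k·d / √(1 + k² − 2ρk), against d / √(2(1 − ρ)) with equal windows.

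Take d = 0.4, ρ = 0.5 and W = 30, so k = 0.233. Mixed windows give 0.0933/√(1 + 0.0544 − 0.2333) = 0.10; equal windows give 0.4/√1 = 0.40. With 52 per arm, power is about 8% against about 53%. Over ρ from 0.3 to 0.7 and W of 28 or 30, mixed-window power stays at 7–9%. The T0 count dominates the score. An analysis of the T1 value with T0 as covariate avoids this dilution: its standardised effect is 0.4/√(1 − 0.25) = 0.46.

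**4. The symptom scales.** Their ranges are unchanged, and the protocol gives nothing from which to estimate a window effect. The direction of the problem is clear; its size is unknown.

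**The case against.** The strongest reply is that the aims (section 3.1), the hypotheses (section 3.3) and the analysis (section 7) are all comparisons between arms. Both arms answer the same questions, so the artefact cancels. This stands for T1. A reader might infer from the mismatch that the estimated LiON effect is biased; step 1 of the check shows that it is not. The reply does not rescue improvement from baseline at T2, where no untreated arm remains. Comparisons of T1 with T2 are unaffected, since both use the past week.

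A reader might also infer that the mismatch weakens the T0–T1 correlation and so costs precision. The document does not support this. It gives no correlation, and the sign is open because a longer baseline window averages out short-term noise. In the constant-rate day-count model above, the variances are 28.0 (30 days) and 2.24 (7 days). The month–week covariance is 5.6, so r = 5.6/√(28.0 × 2.24) = 0.71. The week–week correlation is 1.307/2.24 = 0.58. Here the mixed windows give the higher correlation; real drift from week to week could reverse that.

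Three further limits stand:

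- The 75–77% fall concerns two secondary items only.
- Section 7 names its model for distress, not for days. The loss in step 3 holds only if days are analysed as raw change. Rescaling or covariate adjustment may be laid down in an analysis plan that is not at hand.
- Appendix A, which summarises the assessments, is not in the text at hand and might scale the day items. Section 3.2 as written does not.

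A past-week window at T1 sensibly keeps most of the treatment period out of the recall, but that is no reason for a different window at T0.

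**Conclusion.** The point holds and is moderate in severity. The stated windows make change from T0 within an arm, the time effect and any claim of improvement from baseline at T2 uninterpretable as real change alone. For the productivity items the artefact is a 75–77% fall at a constant rate, assuming that days are counted over the stated windows without rescaling. For the DASS-21 subscales and the distress score its size is unknown. The LiON versus wait-list contrast at T1 remains valid, and no loss of T0–T1 correlation is claimed.

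**What to change.** Use the same past-week window for all outcome questionnaires at T0, T1 and T2, including the productivity items. Keep any past-month reading needed for eligibility in the screening form. This takes a wording change in the online T0 form and a one-line amendment. The cost is a shorter and slightly noisier baseline snapshot; if daily rates are stable, the baseline will predict T1 somewhat less well.

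For participants already enrolled with a past-month T0:

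- Take the T1 or T2 value as the outcome and use T0 only as a covariate. Allow for which version of T0 was given, for example by a version indicator and its interaction with the T0 score, because the change would otherwise put two different measures into one covariate.
- Express the day items as a proportion of their window.
- Do not interpret within-arm change from T0.

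These analysis steps alone would protect the arm comparison. They would not restore improvement from baseline on the symptom scales, because a past-month score cannot be converted to a past-week one afterwards. The form should therefore be changed before more T0 data are collected.

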3.2.1 Primary outcomes

83 84 Primary outcomes of this study include improved symptoms of depression, anxiety, and distress at postintervention (T1) and 1-month follow-up (T2).

85 86

87

88

89

90

Symptoms of depression and anxiety will be assessed using the depression and anxiety subscales (DASS-D and DASS-A, respectively) of the 21-item Depression Anxiety Stress Scale (DASS-21; Lovibond & Lovibond, 1995). The DASS-D and DASS-A each contains 7 items that asks participants about their symptoms of depression and anxiety, respectively, using a 4-point Likert scale (from "did not apply to me at all" [o] to "apply to me very much, or most of the time" [3]). The final score for each subscale was generated by multiplying the sum of the individual items by a value of 2, yielding a score range from 0 to 42, with a higher score indicating higher severity.

95

96

Symptoms of distress will be assessed using 6 items from the Kessler Kessler Psychological Distress Scale (Kessler et al., 2002). Items were rated on a 5-point Likert scale (from "none of the time" [0] to "all of the time" [4]) and summed to generate the final distress score. The total score ranges from 0 to 24, with a high score indicating greater distress.

97 98 99

100

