4.1 Study design and randomisation

This study will adopt an open labelled wait list RCT design (**Figure 1**). Participants will be randomly assigned using a computer-generated sequence into either the (i) low-intensity online intervention (LiON) group (n = 60) or (ii) wait list control (WLC) group (n = 60) in a 1:1 ratio. This study design was adopted to ensure all participants will be able to receive LiON during the period of this study.

Those randomised to the LiON intervention group will first receive the 4-week LiON, with generic self-help tips provided to each participant before completing the T2 assessment. Meanwhile, those randomised to the WLC group will first receive generic self-help tips for a period of 4 weeks, followed by the 4-week LiON before completing the T2 assessment.

Random blocks will be used for randomisation.

^aDuring the review session, the trained interventionist will discuss the concerns and needs of the potential participant to determine the goal of the 4-week LiON sessions, ensure the potential participant meets the inclusion and exclusion criteria of the study, and provide initial briefing about the LiON (including module structure, components of focus).

Figure 1. Flow of the study recruitment and assessment process.

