4.2.3 Generic self-help tips

178 179 180

All participants will also be provided with generic self-help tips. For those in the LiON intervention group, these self-help tips will be provided after the 4-week LiON. For those in the WLC group, these self-help tips will be provided during the first 4 weeks after randomisation.

181 182 183

These generic self-help tips will include general advice on what one can do to improve their conditions. Content of these tips may include the following:

184 185

187

- Breathing exercises
- 186
- Exercise Sleep
- 188
- Reduce mobile phone use

Mindfulness-based exercises

189 190 191

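### T2 is a primary time point for a LiON-versus-control question, but by T2 the wait-list arm has also had LiON

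*Protocol*

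**What the plan says.** **Primary time points.** Section 3.2.1: "Primary outcomes of this study include improved symptoms of depression, anxiety, and distress at postintervention (T1) and 1-month follow-up (T2". Both visits have primary status.

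**The question.** Section 3.3: "Those in the LiON group, as compared to the control group, will show greater reductions in" the listed symptoms. The aims in section 3.1 are framed the same way. Neither section limits the comparison to T1.

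**Treatment before T2.** Section 4.1: "those randomised to the WLC group will first receive generic self-help tips for a period of 4 weeks, followed by the 4-week LiON", and T2 comes after that course. The stated reason for the design is that every participant should receive LiON within the study. For the other arm, section 4.2.3 says: "For those in the LiON intervention group, these self-help tips will be provided after the 4-week LiON".

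**Visit labels.** Section 3.2: "All measures of this study will be conducted at baseline, i.e., pre-intervention (To), post-intervention (T1), and 1-month follow-up (T2". The label for T2 is the same in both arms.

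**Analysis.** Section 7: "Repeated measure ancova model will be used to compare the changes of distress level between two groups", adjusted for variables that differ at baseline. It does not say which visits enter the model or which term is tested.

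**The concern.** A primary LiON-versus-control time point needs a control group at that time. At T2 there is none, because the wait-list arm has completed the same 4-week intervention.

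Two things are at stake. The first is interpretation. If LiON works, the wait-list arm should improve between T1 and T2 and the gap between arms should narrow. A null result at T2 could then be read as failure of an intervention that works. The second is power. Any test that pools T1 and T2 into one group effect averages the T1 effect with a T2 difference that the design itself is expected to shrink.

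**Working it through.** **Step 1. What each arm has received**

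| Visit | LiON arm | Wait-list arm | Contrast |
|---|---|---|---|
| T0 | nothing | nothing | none |
| T1 | LiON | tips | LiON versus tips |
| T2 | LiON, then tips | tips, then LiON | immediate versus delayed LiON |

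T2 is a 1-month follow-up after LiON only in the LiON arm. In the wait-list arm it is the reading after that arm's own LiON course. This step uses only sections 3.2, 4.1 and 4.2.3 and needs no assumption.

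**Step 2. Inputs for an illustration of size**

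The protocol gives no figure for the T2 contrast, so there is none to reproduce. From section 6: n = 52 per arm (N = 104) and alpha 0.05. Assumed:
- two-sided testing;
- equal correlation r = 0.5 between visits, outcome SD 1;
- T1 effect d = 0.48 SD, chosen because it gives a baseline-adjusted T1 test about 80% power;
- a T2 difference of k × d, with k = 1 (persists), 0.5 (half catch-up) or 0 (full catch-up).

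Powers for single contrasts use the noncentral t distribution with 101 df.

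**Step 3. T1 alone, and T2 alone**

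SE = √[(2/n)(1 − r²)] = √[(2/52)(0.75)] = 0.170.
- T1: 0.48/0.170 = 2.83, power 80%.
- T2, half catch-up: 0.24/0.170 = 1.41, power 29%.
- T2, full catch-up: 0, so the rejection rate is alpha, 5%.

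**Step 4. Group effect averaged over T1 and T2, baseline-adjusted**

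Effect = d(1 + k)/2. SE = √[(2/n) × ((1 − r²) + (r − r²))/2] = √[(2/52)(0.5)] = 0.139.

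| T2 difference | Averaged effect | Effect/SE | Power |
|---|---|---|---|
| persists | 0.48 | 3.46 | 93% |
| half catch-up | 0.36 | 2.60 | 73% |
| full catch-up | 0.24 | 1.73 | 40% |

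Under full catch-up the averaged test needs (0.5/0.5²)/0.75 = 2.7 times the N of a T1-only test. At r = 0.7 the factor is (0.36/0.5²)/0.51 = 2.8. This ratio does not depend on d.

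**Step 5. Group-by-time interaction over T0, T1 and T2 (2 and 204 df)**

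Noncentrality λ = (N/4) × SS/(1 − r), where SS is the sum of squared deviations of the three group differences from their mean.
- Persists (0, 0.48, 0.48): SS = 0.1536, λ = 26 × 0.1536/0.5 = 7.99, power 71%.
- Half catch-up (0, 0.48, 0.24): SS = 0.1152, λ = 5.99, power 58%.
- Full catch-up (0, 0.48, 0): SS = 0.1536, λ = 7.99, power 71%.

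Full catch-up costs this test nothing, because the first and third patterns have the same spread. Its problem is meaning. If the wait-list arm overtook by a quarter of the T1 effect (0, 0.48, −0.12), then SS = 0.2016, λ = 10.48 and power rises to 83%, although T2 would favour the wait-list arm.

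**Step 6. Sensitivity**
- d = 0.48, r = 0.7: T1 alone 92%; average 98% if the effect persists and 52% with full catch-up.
- d = 0.2 (section 6's 0.4 halved, read as a standardised mean difference, which the protocol does not state), r = 0.5: T1 alone 21%; average 30%, 19% and 11% for k = 1, 0.5 and 0.

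**The case against.** Three points can fairly be made for the plan.

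**The analysis is not fixed.** A reader might infer that including T2 dilutes the repeated-measures test as such. The protocol does not support that. Section 7 names neither the visits nor the term, and a statistical analysis plan, not shown, may settle both. For a group-by-time interaction, a natural reading of comparing changes, full catch-up loses no power. It would also be wrong to read its 71% as a fall from the 80% of the T1 test: the two tests differ, and a T0–T1 interaction alone would have 68%. This objection stands, so dilution is claimed only for a pooled group effect and for T2 tested alone, with a loss in the interaction only under partial catch-up.

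**The sizes rest on assumptions.** The 0.48 SD effect, the correlations and the catch-up fractions are not in the protocol. A reader might infer that a sound 80% test is cut to 40%, but on section 6's halved effect, read as a standardised difference, even T1 alone has about 21%. This also stands, and the powers are illustrations only.

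**T2 is still a randomised comparison.** It is tempting to call it biased. It is better described as a valid estimate of a different quantity, immediate versus delayed LiON. That T2 could favour the wait-list arm is possible, but nothing in the protocol quantifies it.

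None of this removes the core. Section 3.2.1 does not itself call T2 a between-group test, but sections 3.1 and 3.3 make that the natural reading, and nothing confines the comparison to T1. A later plan could resolve this only by overriding section 3.2.1.

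**Conclusion.** The point holds in this form. The protocol makes T2 primary for a LiON-versus-control question at a visit where no arm is without LiON. That follows from its own text, without assumptions. The randomised T1 contrast of LiON with tips is intact and can answer the question.

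The effect on power is conditional. If one group effect is pooled over T1 and T2, full catch-up halves it and raises the required N to about 2.7 to 2.8 times that of a T1-only test, for r between 0.5 and 0.7. If T2 is tested alone under full catch-up, the rejection rate is alpha. If the interaction is tested, power may be unaffected, but a significant result does not show that LiON is superior at T2. Which case applies cannot be told from section 7. The matter should be settled before analysis because it concerns the primary outcome.

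**What to change.** In section 3.2.1, name T1 as the only primary between-group time point. In section 7, define the primary comparison as the baseline-adjusted group difference at T1, by ANCOVA or as the T1 contrast of the repeated-measures model.

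Report T2 in one or more of three ways: maintenance from T1 to T2 within the LiON arm; change from T1 to T2 within the wait-list arm, stated to be uncontrolled; or a between-arm comparison explicitly labelled immediate versus delayed LiON. Make no LiON-versus-control efficacy claim from T2. In section 3.2, note that T2 is a 1-month follow-up only for the LiON arm.

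The cost is wording. Visits, care and the commitment that all participants receive LiON are unchanged. The trial gives up a controlled 1-month claim, which the design does not support in any case.
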